2. STUDY PROCEDURES

a. Procedures

This study protocol is similar in parts to previously approved protocol, "Accelerometers in spine surgery study," for which [name] (Co-PD on current proposal) is the PD.

All English-speaking adult patients (≥ 18 years old) who are undergoing elective spine surgery (excluding patients with spine trauma, tumors, or infection) for Cohort 1 or are undergoing any back treatment for Cohort 2 by neurosurgery attending physicians at Stanford ([name], [name], [name], [name], [name], [name]) will be eligible for participation in this study.

All participants in Cohort 1 and Cohort 2 will receive our standard of care.

In Cohort 1, percentage for random assignment to each group is 50%. Those assigned to the "intervention" (i.e., the Apple Watch) will receive instructions on how to use the activity section within the Watch. The participants will either have their mobility data submitted via the previously approved app Neurocoach. The intervention group will wear the Apple watch 2-6 weeks pre-operatively as well as at least 6 months post-operatively (may continue to wear as long as 12 months). The control group will not. Patients in the interventional group receiving an Apple Watch may be asked to come in for a training and set-up visit at clinic. Parking passes will be provided for this visit.

All patients in Cohort 1 will be seen in follow-up clinic as per standard of care (4-6 weeks, 3 months, 6 months, and 12 months post-operatively). At each time point, all patients will complete standardized quality of life questionnaires (several of which are already incorporated in our postoperative clinic) and an additional study-specific questionnaire regarding satisfaction with their care and recovery.

In Cohort 2, all participants will receive an Apple Watch and instructions on how to use the activity section within the Watch. The participants will have their mobility data submitted via the previously approved app Neurocoach. Participants will wear the Apple Watch for 2-3 weeks. Participants will complete standardized quality of life questionnaires (several of which are already incorporated in our postoperative clinic) at the beginning and end of the 2-3 week study. This cohort will have their pain monitored daily using brief questionnaires.

b. Procedure Risks

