Our protocol does not change the standard of care for any patient. It provides a supplementary intervention for half of our patients. The intervention is using a wearable activity monitor device (the Apple watch), which is a minimal risk.

c. Use of Deception in the Study

Deception will not be used.

d. Use of Audio and Video Recordings

Audio or video recording will not occur.

e. Alternative Procedures or Courses of Treatment

Standard of care will not be withheld. Our study does not involve alternative procedures or treatments.

f. Will it be possible to continue the more (most) appropriate therapy for the participant(s) after the conclusion of the study?

All patients will undergo standard of care for their spine surgery before, during, and after the study.

g. Study Endpoint(s)

For Cohort 1, the study endpoint will be 12 months postoperatively. Following enrollment during the pre-operative visit, we will see patients in clinic during their standard postoperative visits, at 4-6 weeks, 3 months, 6 months, and 12 months post operatively. All patients will complete the Stanford Spine quality of life questionnaires, as per the standard of care, at all postoperative visits. Patients with the Apple Watch will also fill out a paper questionnaire assessing satisfaction with the Apple Watch (all questions are included in attachment).

As participants reach the 12-month study period, we will conduct ongoing analysis of the data. If we observe clear statistically significant and clinically significant superiority in one group, the study will be terminated prior to the projected total participant population has been enrolled. If there are no such differences noted, the Cohort 1 will terminate after the all patients have had their 12-month postoperative visit, likely July 2023.

For Cohort 2, the study endpoint will be 2-3 weeks after enrollment and Apple Watch setup. If we observe clear statistically significant and clinically significant changes, the study will be terminated prior to the projected total participant population has been enrolled. If there are no such differences noted, the Cohort 2 will terminate after all patients have completed the study, likely August 2021.

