4. PARTICIPANT POPULATION

a. Planned Enrollment

Cohort 1:

- (I) around 200 patients total at Stanford Neuroscience Health Center and at Stanford Medicine Orthopaedic Spine Center
- (II) around 200 patients total at Stanford Neuroscience Health Center and at Stanford Medicine Orthopaedic Spine Center (the cohort will not include participants from any other non-Stanford sites)

100 patients will be in the control arm - no Apple Watch or app; 100 patients will be in the intervention arm - will receive Apple Watch and will download app.

A few additional subjects may be enrolled so as not to delay the completion of the trial. Surgery for a subject may change to several weeks later or subjects may decide not to do surgery. The target in each cohort will remain at about 100 subjects.

Participants will be adults (greater than or equal to 18 years old) who will be undergoing elective spine surgery at Stanford University Hospital by a Stanford Neurosurgery or Orthopaedic Spine attending physician. The reason for using such participants is to be able to effectively assess long-term mobility and satisfaction outcomes of patients who have undergone spine surgery who will be using Apple Watch in addition to the standard of care.

Cohort 2:

- (I) 15 patients total at Stanford Neuroscience Health Center
- (II) 15 patients total at Stanford Neuroscience Health Center (the cohort will not include participants from any other sites)

Participants will be adults (greater than or equal to 18 years old) who are undergoing any back treatment by a Stanford Neurosurgery attending physician. The reason for using such participants is to be able to effectively assess short-term mobility and satisfaction outcomes of patients experiencing back pain who will be using Apple Watch in addition to the standard of care.

b. Age, Gender, and Ethnic Background

All participants will be adults (greater than or equal to 18 years old). There is no other specification in terms of gender or ethnic background.

c. Vulnerable Populations

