The greatest risk to patients in this study will be confidentiality of identifiable information. All electronic devices (e.g., computers, hard drives, thumb drives, etc.) that contain identifiable patient information will meet Stanford School of Medicine security standards; additionally, the devices will be password-protected and encrypted. The patient's activity data will be downloaded to Stanford Research IT-approved Google Firebase storage. All data will be stored per approved Research IT / DRA protocol. No data will be shared with industry partner providing part of the funding.

d. Study Conclusion

For Cohort 1, as participants reach the 12-month study period, we will conduct ongoing analysis of the data. If we observe clear statistically significant and clinically significant superiority in one group, the study will be terminated prior to the projected total participant population has been enrolled. If there are no such differences noted, the study will terminate after the all patients have had their 12-month postoperative visit, likely June 2022. We do not expect adverse effects but will be able to identify them at postoperative visits (4-6 weeks, 3 months, 6 months, and 12 months post-operatively) and intervene if needed.

For Cohort 2, we will conduct ongoing analysis of the data. If we observe clear statistically significant and clinically significant changes, the study will be terminated prior to the projected total participant population has been enrolled. If there are no such differences noted, the Cohort 2 will terminate after all patients have completed the study, likely August 2021.

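### Cohort 2 may be stopped early on significance, with looks, level, boundary, clinical threshold and outcome all unstated: the error rate cannot be determined, and an early-stopped estimate would be exaggerated

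*Protocol*

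**What the plan says.** Section 4.a sets the size of Cohort 2: "15 patients total at Stanford Neuroscience Health Center". There is one arm (section 2.a): "In Cohort 2, all participants will receive an Apple Watch and instructions on how to use the activity section within the Watch". Questionnaires are completed "at the beginning and end of the 2-3 week study", and section 2.g adds: "For Cohort 2, the study endpoint will be 2-3 weeks after enrollment and Apple Watch setup".

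The stopping rule stands in 2.g and again in 5.d: "If we observe clear statistically significant and clinically significant changes, the study will be terminated prior to the projected total participant population has been enrolled". Section 5.d puts before it: "For Cohort 2, we will conduct ongoing analysis of the data". Section 2.g does not repeat that lead-in for Cohort 2. If no such changes are seen, the cohort runs until all patients have finished.

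Neither section gives the number or timing of looks, a significance level, a boundary, a size of change that counts as clinically significant, or the outcome to which the rule applies.

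**The concern.** This is a data-driven stopping rule stated in mandatory terms. Two consequences follow from using such a rule without fixed looks and thresholds.

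- Each additional look at accumulating data is another chance to cross the line when nothing has changed, so the overall false-positive rate exceeds that of a single test under the same criterion.
- A cohort that stops because its change looks large reports an estimate selected for being large. In a cohort of 15 this selection is strong, and the truncated sample also loses precision.

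Several measures could trigger the rule (steps, distance, heart rate, questionnaires, daily pain), and none is designated. Early stopping also gains little: follow-up lasts 2-3 weeks, the protocol rates the risk as low, and every Cohort 2 patient receives the device anyway.

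**Working it through.** **Nothing to reproduce.** The protocol gives no alpha, power, effect size, SD or sample-size derivation for Cohort 2, so the check is a simulation under stated assumptions.

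**From the protocol.** Maximum n = 15 (4.a). Single arm, with questionnaires at start and end (2.a). Endpoint at 2-3 weeks (2.g), so results can arrive while enrolment is open.

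**Assumed.** One outcome; a normally distributed paired change, measured in units of its SD; a two-sided one-sample t-test at each look. With t_n = mean_n / (s_n/√n), the cohort stops at the first look where |t_n| > t(1−α/2, n−1) and, if a clinical threshold c is imposed, |mean_n| ≥ c. The look schedules, α and c are all assumptions and are varied below. Each scenario has 200,000 simulated cohorts.

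**False-positive rate when the true change is zero (%):**

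| Looks at n = | p<0.05 | p<0.05 and ≥0.5 SD | p<0.05 and ≥0.8 SD | p<0.05 and ≥1.0 SD | p<0.01 |
|---|---|---|---|---|---|
| 15 only | 4.9 | 3.4 | 0.2 | 0.0 | not run |
| 8, 15 | 8.5 | 6.7 | 1.8 | 0.5 | not run |
| 5, 10, 15 | 11.4 | 9.3 | 3.3 | 1.4 | 2.6 |
| 3, 6, 9, 12, 15 | 15.4 | 13.0 | 5.5 | 2.8 | not run |
| every patient from 5th | 16.4 | 14.0 | 5.4 | 2.0 | 4.2 |
| every patient from 3rd | 20.2 | 17.5 | 8.2 | 4.2 | 5.4 |
| every patient from 2nd | 23.4 | 19.7 | 9.9 | 5.4 | not run |

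On the statistical criterion alone, the multiple of 5% runs from 8.5/5 = 1.7 to 23.4/5 = 4.7. Within each p<0.05 column, repeated looks raise the rate above that of one analysis under the same criterion; with the 0.5 SD threshold, for example, 9.3/3.4 = 2.7 times. What the threshold changes is the absolute level.

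**Why the threshold matters so much.** The smallest observed change that reaches p<0.05, in units of the observed SD, is t(0.975, n−1)/√n:

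- n = 5: 2.776/2.236 = 1.24
- n = 10: 2.262/3.162 = 0.72
- n = 15: 2.145/3.873 = 0.55

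A 0.5 SD threshold lies below all three and seldom binds. A threshold of 0.8 SD binds at 10 and 15 patients.

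**Exaggeration when stopped before 15 (p<0.05 per look).** Ratio = mean estimate in early-stopped cohorts / true change:

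| True change | Looks 8, 15 | Looks 5, 10, 15 | Every patient from 5th | Every patient from 3rd |
|---|---|---|---|---|
| 0.3 SD | 0.776/0.3 = 2.59 | 0.763/0.3 = 2.54 | 0.709/0.3 = 2.36 | 0.704/0.3 = 2.35 |
| 0.5 SD | 0.895/0.5 = 1.79 | 0.892/0.5 = 1.78 | 0.823/0.5 = 1.65 | 0.844/0.5 = 1.69 |
| 0.8 SD | 1.042/0.8 = 1.30 | 1.041/0.8 = 1.30 | 0.977/0.8 = 1.22 | 1.009/0.8 = 1.26 |

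Adding the 0.5 SD threshold raises the ranges to 2.47-2.68, 1.69-1.82 and 1.23-1.31, because it selects further for large estimates.

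**The case against.** A reader might infer that the cohort stops at any look reaching ordinary significance, and that its false-positive rate is therefore two to three times nominal. The text does not support this. The rule requires statistical and clinical significance together and qualifies them as clear, and no alpha appears anywhere. The multiple of two to three fits about three to five looks at p<0.05 with no clinical threshold (11.4-15.4%). With a 0.8 SD threshold, or with p<0.01 per look, the rate is near or below 5% for most of the schedules examined.

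Nor can one say that a significant result in so small a cohort would nearly always look clinically large. The figures of 1.24, 0.72 and 0.55 are in SD units, and the protocol gives neither an SD nor a clinically important difference on any scale.

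Other objections carry weight. No accrual rate is given for Cohort 2, and fast enrolment could leave few or no looks before it is full. A statistical analysis plan that is not at hand may set looks and a boundary, so their absence alone is no fault. No confirmatory hypothesis or error rate is stated for this uncontrolled cohort, and a null of exactly zero change is doubtful in patients under treatment.

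Stopping could also be retained with error control: about 0.021 per look for three looks (5, 10, 15), or 0.012 for a look after every patient from the 5th, holds the overall rate at 5%. That repairs the first problem but not the second: a stricter per-look level still stops only on extreme estimates.

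What remains is that 2.g and 5.d themselves prescribe termination on significance, and 5.d prescribes open-ended analysis. Neither refers to another document for the limits.

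**Conclusion.** The point holds in a limited form. The protocol fixes a data-driven stopping rule for Cohort 2 whose error rate cannot be determined from what it states. Any inflation figure is conditional: for one outcome at p<0.05 per look, about 11% (looks at 5, 10, 15) to 16% (every patient from the 5th), falling to 9% and 14% with a 0.5 SD clinical threshold, to 3% and 5% with 0.8 SD, and to 2.6% and 4.2% at p<0.01 without a threshold. Choosing among several outcomes would add to these.

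The overstatement of early-stopped results is the firmer part. It appeared under every schedule and true change examined, from about 1.2 to 2.6 times at p<0.05, and was slightly larger with the 0.5 SD threshold. It shrinks as the true change grows.

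The consequence is modest because the cohort is small and has no control group, but the change is worth making because it is nearly free.

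**What to change.** In 2.g and 5.d, delete the early-termination sentence for Cohort 2. In 5.d, also remove the commitment to ongoing analysis of that cohort, and adjust the sentence that follows in each section. Insert in both: *Cohort 2 enrols 15 patients and is analysed once, after the last patient completes the 2-3 week period; changes are reported with confidence intervals.* The provisions in 5.c for hazards and for removing a participant are untouched.

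A single analysis at 15 gives the nominal rate for one outcome (4.9% simulated) and removes the selection caused by early stopping. It does not address the lack of a control group, which is a separate matter. The cost is wording in two sections, and the cohort cannot end a few patients early.

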6. BENEFITS

We posit that patients with spine pathology who undergo surgery or are experiencing back pain will improve their physical activity level and feel more satisfied with their quality of life when wearable activity monitors are used to provide feedback on physical activity and when such data is used to initiate discussions about activity with their spine surgeon. Our hope is that using a commercially available device will make the results of our study applicable to future patients who may also have the Apple Watch (or other commercially available activity monitors).

7. PRIVACY AND CONFIDENTIALITY

All participant information and specimens are handled in compliance with the Health Insurance Portability and Accountability Act (HIPAA) and privacy policies of Stanford University, Stanford Health Care, and Stanford Children's Health.
